1.23 PLANNED RECRUITMENT RATE

[figure not shown]

Figure 2 Target Recruitment Rates

With at least 28 centres, set up over 18 months at a rate of 1.5 centres per month, and a recruitment rate of 0.7 pts/site/month, the target sample size of 630 patients will be achieved in 41 months. As a contingency, slower recruitment at 0.5 pts/site/month would require 35 sites and 48 months to complete recruitment (above Figure 2).

The timetable is: Start Date 1st October 2023. Months 1 – 4 set-up, months 5 – 45 recruitment, months 46 – 93 follow-up to last patient last visit (LPLV), months 94 – 97 data cleaning, data lock, months 97 – 101 analysis, site closedown, dissemination.

1.24 PARTICIPANT IDENTIFICATION

All eligible patients will be identified by the clinical care team and provided with a Participant Information Sheet (PIS). This will be followed up with further telephone or face-to-face discussion by a clinician and/or clinician researcher should the patient be agreeable.

1.24.1 In the Elective Setting

Potentially eligible patients will be identified from clinic lists or Heart Team meetings, and contacted by a clinician and/or clinician researcher either during clinic attendance or by post, should they have been spoken to about research at the hospital prior to the posting of this information. All eligible patients who are approached will be given the PIS. The patient will then be offered an opportunity for face-to-face discussion of the PIS and informed consent, if appropriate, at a scheduled clinic visit. Alternatively, the patient may choose to speak to a local research team member via telephone having received the PIS to discuss it at a later date. Written or electronic consent will be obtained in the latter scenario to protect the participant from burden from additional research visits. Patients and their carers may take more than one visit to decide upon participation. Subsequent visits can be over the telephone or via a Microsoft Teams call (or similar platform) to again protect the participant from additional burden.

1.24.2 In the Urgent Setting

Potentially eligible patients will be given the PIS as soon as possible after the Heart Team has determined suitability for both PCI and CABG. The patient will speak to a clinician and/or local clinician research team member (face-to-face) who will discuss the PIS and seek consent if the patient is agreeable and able to provide consent. There will be no requirement that a patient has the PIS for a minimum duration (please see section 1.25). Despite the short notice, it is important to include these patients for the applicability of the trial findings since about 40% of patients having coronary artery bypass, and 70-80% of patients undergoing PCI are admitted as urgent cases. These patients often have left ventricular dysfunction and are an important target population for the trial. Written informed consent will be obtained during the hospital admission prior to randomisation.

1.25 CONSENT

Prior to participation in the trial, patients will be required to provide informed consent. It will be possible to do this either via written informed consent or electronic consent using the REDCap consent module. The PIS, ICF(s) and any amendments will be submitted and approved by a Research Ethics Committee (REC), the Health Research Authority (HRA), Study Sponsor and the local Trust Research and Development/Innovation (R&D/I) department prior to implementation. The process of consent by either method will require individual discussion with the patient.

There is no requirement that a patient must have the PIS for a minimum duration prior to consent in either setting and by either method, considering the often-urgent requirement for revascularisation in people presenting with ACS. However, every effort should be made to maximise the amount of time the patient has for consideration of trial enrolment.

Written or electronic versions of the PIS and ICF will be presented to the participant detailing no less than: the exact nature of the trial; the implications and constraints of the protocol; the known side effects and any risks involved with taking part. It will be clearly stated that the participant is free to withdraw from the trial at any time for any reason and without prejudice to future care, and with no obligation to give the reason for withdrawal.

Having considered the information, the patient may give their consent straight away. Alternatively, if they wish to consider the information and have the opportunity to ask questions of the Investigator, their GP or other independent parties to aid their decision of whether they wish to participate in the trial, they will be afforded this time to make their decision (setting dependent).

The person who obtained consent must be suitably qualified and experienced, and have been authorised to do so by the Principal Investigator (PI) as delegated on the Delegation of Authority and Signature Log for the trial. In this particular trial, consent can be sought by Research Nurses (if local regulations allow), or by the participating surgeons or surgical trainee, if all appropriately delegated to do so. Eligibility must be confirmed by a delegated clinician and / or clinician researcher on ResearchApp™ (HealthBit®).

1.25.1 Written Informed Consent

Written Informed Consent will be obtained by means of participant dated signature and dated signature of the person who presented and obtained the informed consent. The original signed ICF will be

retained at the trial site within the Investigator Site File (ISF). A copy of the signed ICF will be provided to the participant and a copy retained in the participant medical notes.

Participant identifiers will be allocated using the Sealed Envelope randomisation system and recorded on the corresponding written ICFs in the space provided.

1.25.2 Electronic Consent

The trial will offer the option of electronic consent as an alternative to face-to-face methods. It is recognised that not everyone will be able to utilise this method due to technology access and so this option is only intended as an alternative to face-to-face consent. This model will however allow for minimisation of participant burden as well as a resilient option. The electronic consent process will mirror the content of the paper documents, including a localised electronic PIS, and will be supported by the REDCap electronic consent module. The ICF will reflect the same options but participants will record consent by marking a radio button for each consent option as opposed to initialling boxes as reflected by the paper method. This process will be supported by a Video/Telephone Consent Form to be completed by the researcher or delegated individual at site performing consent, confirming that the participant has understood the information and consent process. The electronic consent system will only be accessible by appropriate personnel active on the trial who will only be able to view consents for the site with which they are associated. The system will notify of any errors in a submitted consent form which can be rectified by the participant only, as well as produce a PDF for the participant, research and medical records upon which sites should record the participant identifier once the participant has been randomised using Sealed Envelope. Where appropriate, electronic consent will be supported either over the telephone or by videocall between the participant and the clinician/researcher. Sites wishing to utilise electronic consent should nominate one person to undertake the Site Set-up Exercise and anyone else wishing to use the system to issue consent invitations to potential participants should read the training document. Following this, anyone wishing to be issued with a REDCap account to invite potential participants using a nominated email address should be delegated this specific activity separate to, but in addition to, that of performing consent. Whilst the option of electronic consent will be offered to reduce participant burden, baseline assessments must still be conducted in person following consent and ahead of randomisation to allow for the required clinical measures to be performed.

1.26 METHOD OF IMPLEMENTING THE RANDOMISATION/ALLOCATION SEQUENCE

1.26.1 Randomisation

Randomisation with allocation concealment will utilise a centralised, web-based system (Sealed Envelope Ltd, London, UK). Participants will be randomised on the day of consent in a 1:1 ratio to either CABG or PCI stratified by centre and clinical presentation; acute versus chronic coronary syndrome.

The participant's initials, date of birth, and sex will be entered into the randomisation system which will generate the participant's randomised allocation (PCI or CABG) and unique participant identifier (Trial ID).

1.27 ALLOCATED TREATMENT

Revascularisation appropriateness and feasibility will be confirmed by the local Heart Team (a minimum of an interventional cardiologist and a cardiac surgeon). Revascularisation should be performed as soon as dictated by clinical urgency but no more than 18 weeks (+/- 28 days) from randomisation for elective cases or 6 weeks from randomisation for urgent/ACS cases (+/- 28 days).

Complete revascularisation of all viable myocardium is the goal for all patients. Revascularisation will be attempted on/for significant lesions in major coronary vessels/side branches as planned by the local Heart Team, with the general recommendation of stenotic/occluded vessels with diameter >1.5mm. As per contemporary ESC treatment guidelines, physiological or non-invasive functional confirmation of haemodynamic severity should be sought in any vessel that has <90% stenosis. As a measure of process, and to estimate completeness of revascularisation, the British Cardiovascular Intervention Society Jeopardy Score (BCIS-JS) will be calculated at baseline and after final stage PCI or CABG using the www.BCIS-JS.com calculator.

1.27.1 Co-enrolment

Co-enrolment is permitted in line with the inclusion and exclusion criteria of the STICH3-BCIS4 protocol as well as the corresponding trial being considered for co-enrolment with.

1.27.2 Percutaneous Coronary Intervention

For patients randomised to PCI, contemporary best practices should be used. These include:

1. Physiological assessment of stenosis severity (with invasive fractional flow reserve (FFR) and/or angio-based FFR estimation) in all coronary stenoses with a visual stenosis severity $\leq 90\%$ and the use of intracoronary imaging (with intravascular ultrasound (IVUS) or optical coherence tomography (OCT) to document the final result, as a minimum, but to guide all aspects of the procedure).
2. IVUS/OCT assessment post stent implantation for optimisation of stent deployment is mandated with the following goals:
 - a) A relative stent expansion of $> 80\%$ (minimum stent area (MSA) divided by average reference lumen area) should be obtained in routine clinical practice.
 - b) An MSA of $> 5.5\text{mm}^2$ by IVUS and over 4.5mm^2 by OCT should be achieved in on-left main lesions wherever possible.
3. IVUS/OCT use pre-PCI is recommended (but not mandated) with the following guidelines:
 - a) Plaque preparation based on pre-procedural IVUS/OCT. Rotational atherectomy or cutting, scoring balloon, shockwave should be considered if a $>270^\circ$ arc of superficial calcium is evident in IVUS or OCT.
 - b) Selection of stent size dimensions.
 - i. In *non-bifurcation* stenosis: the chosen stent diameter should match the distal vessel diameter or area.
 - ii. In *bifurcation* stenosis: stent diameter should match distal (daughter) branch, with mandatory post-dilation of the proximal (mother) segment and polygon of confluence (POC) with a larger balloon size according to IVUS/OCT imaging (Proximal Optimisation Technique procedure, POT). IVUS/OCT should also be used to guide stent length by identification of proximal and distal landing zones that have minimal or no atheroma.
 - iii. Incomplete stent expansion: aim to achieve MSAs as above by post dilation.
 - iv. Incomplete stent apposition. A non-compliant balloon sized IVUS/OCT to vessel luminal diameter or area will be used in segments with malposition.
4. Transradial access is strongly encouraged where there is no contraindication.
5. New-generation drug-eluting stents, atherectomy and/or intravascular lithotripsy for extensive calcification, recommended bifurcation techniques are strongly encouraged (23).
6. Where patients have one or more chronic total occlusions supplying viable myocardium, the participant should only be enrolled if the necessary expertise in CTO-PCI is available, if the Heart Team consider the risk/benefit balance favours CTO intervention.

7. Staging PCI is permitted where the cardiologist feels that this is in the patient's best interest, but the intention to stage must be documented at the first procedure.
8. Mechanical circulatory support should be reserved for bailout in case of mechanical complication of the PCI or developing cardiogenic shock, unless new evidence arises during the course of the trial to indicate benefit to routine use.

Details of physiological, intracoronary imaging, and advanced percutaneous methods will be recorded in the CRF as will mechanical circulatory support.

1.27.3 Coronary Artery Bypass Grafting

The left internal thoracic artery is the preferred graft for the LAD. The choice of performing on-pump or off-pump surgery will be at the discretion of the operator based on the local expertise. Perioperative management of cardiopulmonary bypass will follow local protocols. Minimally invasive or hybrid revascularisation is not allowed. The use of multi-arterial graft, intraoperative echocardiography, epi-aortic ultrasound, and anaesthetic technique will be tailored to the patient and the centre, with best contemporary practices encouraged. Details of the surgical procedure will be captured in the eCRF. Valvular heart disease indicating the need for mechanical repair/replacement or any other structural cardiac surgery (e.g. LV aneurysm resection). Planned major concomitant cardiac surgery is an exclusion criterion, however unplanned concomitant surgery will occur as part of normal care and will be recorded.

1.27.4 Concomitant Therapies

All participants will receive antiplatelet therapy and anticoagulation as defined by the most recent international practice guidelines (24-26). **Guideline-directed** medical therapy for HFrEF (27) may evolve during the course of BCIS-4 recruitment and follow-up but currently includes 1). Beta-blockers 2). Angiotensin-converting enzyme inhibitors (ACE-I), or angiotensin receptor blockers (ARB) or sacubitril/valsartan 3). Mineralocorticoid receptor agonists (MRA) 4). SGLT2 inhibitors adjusted to optimally tolerated doses unless contraindicated. We will mandate that every effort be made to establish patients on optimally-tolerated medical therapy for HFrEF, however, as decisions regarding revascularisation are generally made at the time when patients undergo angiograms and after the Heart Team makes a decision that there is equipoise between PCI and CABG, in some cases optimisation of medical therapy may occur after the revascularisation procedure.

We will strongly encourage the research teams to refer patients to their local heart failure team for ongoing management. Diuretics and NHS DigiTrials use will be individualised to patient-specific indications. Implantable cardioverter defibrillators (ICD) and cardiac resynchronisation therapy will be used as per the most contemporary guidelines (28). Medical therapy for secondary prevention of CAD will also be individualised by Heart Teams as per guideline recommendations. Angina will be managed as defined by the Chronic Coronary Syndromes (CCS) practice guidelines (29). Regular heart failure medications will be captured at follow-up visits. Heart failure medications and ICDs/ cardiac resynchronisation therapy (CRT) will be recorded at baseline and follow-up in the eCRF.

1.27.5 Duration of the Intervention

Revascularisation will be completed as per institutional norms after consideration of presentation, access to care, and resources. In ACS, revascularisation should be encouraged to be undertaken during the index admission but patients may be discharged to return for PCI or CABG. If this is the case, revascularisation should be undertaken as soon as dictated by clinical urgency but no more than 6 weeks (+/- 28 days) of randomisation. For non-ACS cases, the assigned treatment should be undertaken as soon as possible after randomisation and no more than 18 weeks (+/- 28 days) later.

Table 1 Schedule of Processes

Assessment	Screening	Baseline Assessment	Index Procedure	Post Procedure until Discharge	3 Months	6 Months ¹	12 Months ¹	6 Months and every 6 Months to 4 Years	Every 12 months to 4 Years ¹	Following LPLV
	-90 to 0	-30 to 0	Day 0	Day of revascularisation procedure until hospital discharge	+/- 28 days after Day 0	+/- 28 days after Day 0	+/- 28 days after Day 0	6 months +/- 28 days after Day 0	+/- 28 days after Day 0	
Informed Consent	X									
Inclusion/Exclusion	X									
Revascularisation and feasibility confirmed by local Heart Team	X									
Pregnancy Test ²	X ²									
Demographics, Height and Weight		X								
Medical/Cardiac History (including long term conditions and severity of cardiac diseases)		X								
Risk Scores (BCIS Myocardial Jeopardy Score and EuroSCORE II)		X		X						
Randomisation		X								
NYHA Class and CCS Class		X		X	X			X		
Kansas City Cardiomyopathy Questionnaire (KCCQ)		X		X	X			X		

Assessment	Screening	Baseline Assessment	Index Procedure	Post Procedure until Discharge	3 Months	6 Months ¹	12 Months ¹	6 Months and every 6 Months to 4 Years	Every 12 months to 4 Years ¹	Following LPLV
	Visit window (days) (± number of days this visit can take place ahead or after its due date)	-90 to 0	-30 to 0	Day 0	Day of revascularisation procedure until hospital discharge	+/- 28 days after Day 0	+/- 28 days after Day 0	+/- 28 days after Day 0	6 months +/- 28 days after Day 0	+/- 28 days after Day 0
Seattle Angina Questionnaire 7 (SAQ-7)		X		X	X			X		
EQ-5D-5L		X ¹			X ¹	X ¹	X ¹		X ¹	
Health Care Resource Use		X ¹			X ¹	X ¹	X ¹		X ¹	
Revascularisation procedures and revascularisation completeness			X							
Procedural Data Collection				X						
Concomitant Medications ³		X ³	X ³	X ³	X ³			X ³		
Clinical Events ⁴			XXXXXXXXXXXXXXXXX ⁴							
Routinely collected data extraction (HES/ONS/NICOR) ⁵										X ⁵

¹ Assessment timepoints included for purposes of Health Economics only (EQ-5D-5L and Health Care Resource Use). Health Economic timepoints, where required, match the time point requirements of the other follow-up questionnaires and should be conducted together. Where a timepoint does not require Health Economics questionnaires to be completed, all other measures should be completed in line with the schedule. ²Women of childbearing potential. ³Includes antiplatelet therapy and anticoagulation (defined by most recent international practice guidelines), statins, and heart failure treatment as per guideline recommendation. ⁴Clinical events from the start of surgery until hospital discharge. The following clinical events will be assessed through review of the patient medical records/chart, and reported in the eCRF from the start of the index procedure until discharge. ⁵Where explicit consent is provided and remains without withdrawal.

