1.20 FOLLOW-UP

Patients will be followed up during their index hospital stay (or stays for planned staged PCI). Primary and secondary outcome measurements will be collected for a minimum follow-up of 4 years and given a 41-month recruitment period will result in a median follow-up length of 5.3 years. Outcome measurements during follow-up (excluding PROMS and 30-day SAEs) will be determined through routinely collected HES/ONS data.

Quality of Life Assessments, and Health Economic Outcomes will be ascertained at baseline, and then using telephone follow-up or self-completion using the ResearchApp™ (Healthbit®) at 3 months, 6 months, 12 months and then annually post randomisation (\pm 28 days) until the end of trial follow-up. Please refer to **Table 1** for further details about follow up visits.

Consent for life-long trial follow-up following completion of this trial's current funded period (i.e., beyond 41 months recruitment + 48 months follow-up period) using routinely collected healthcare data will be obtained.

Consent will be sought for relatives/friends to provide information if and when it is established that the participant is not contactable, has lost capacity or is too unwell, to ascertain what has happened to them. Where available and willing, two alternate contacts should be sought, through the means of the Consent to Contact Form. If it is subsequently determined that the participant has lost capacity or has become too unwell to respond to follow-ups, the research teams will initially attempt contact with the named relative(s)/friend(s) to seek consent using the Personal Consultee Information Sheet, which they may be provided with in advance, and Personal Consultee Declaration form, which can only be signed in the event that the participant has lost capacity. We will also seek consent to notify their general practitioner (GP) of their participation of their participation in the trial.

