1.21 END OF TRIAL

For an individual participant, the end of trial is defined as time of last follow-up visit (4 years post randomisation), participant withdrawal, or mortality, whichever occurs sooner.

Participants will be considered lost to follow-up if there is insufficient information or inability to gather necessary data points required for the trial, although this is expected to be anomalous as data points are routinely collected in standard practice. In the instance where it is not possible to obtain follow-up data for one particular point in time (e.g., 6-month follow-up) the participant should not be considered as lost to follow-up at this point but rather the next follow-up in sequence should be attempted at the relevant time point within the stipulated window (e.g., 12 months). This process should be followed up until the last follow-up visit at which point if no further follow-ups have been completed from timepoint X, then the participant should be considered as lost to follow-up from that timepoint. This should not prevent the performance of NHS Digital (or equivalent) extractions, unless an explicit withdrawal from this element of the trial is communicated.

The length of time covered by routinely collected data extractions will depend on the point at which the participant consented to participation in the trial. For example, a participant recruited early on in the recruitment phase (months 5 – 45) will have more routinely collected data collected until last patient last visit (LPLV) (month 93) than a participant recruited later on in the trial.

On the whole, the definition of end of the trial is the final data lock following any data query resolutions (months 94 – 97, or approximately 8 years). Following this, participants will be informed of the trial study result should they have explicitly requested this by way of informed consent, thus being reflected on the ICF. This will be performed by each recruiting site.

TRIAL PROCEDURES

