1.43 ANALYSIS POPULATION

The primary analysis will be based on ITT principles with the analysis population consisting of all participants who are randomised and compared in the groups to which they were allocated regardless of treatment being received. The per-protocol (PP) population will consist of all participants who underwent revascularisation as randomised, excluding patients who had a major protocol deviation e.g., patients who crossed over, had their allocated treatment changed or discontinued by the treating physician at any time, or withdrew consent.

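### Table 1 dates follow-up visits from the index procedure, while 1.20 and 1.21 date them from randomisation; the two windows share no day once the wait for the procedure exceeds 56 days

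*Protocol*

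**What the plan says.** **Table 1 (Schedule of Processes, under 1.27.5).** Day 0 is the entry for the Index Procedure column, and the next column runs from the day of revascularisation to discharge. Randomisation sits in the baseline column, with a window of -30 to 0. The 6-monthly column, which carries NYHA/CCS class, KCCQ, SAQ-7 and medications, is dated "6 months +/- 28 days after Day 0". The columns that carry EQ-5D-5L and resource use have the same 28-day window after Day 0. Footnote 1 says the health-economic time points "match the time point requirements of the other follow-up questionnaires and should be conducted together".

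**1.20.** Quality-of-life and health-economic outcomes are collected at "3 months, 6 months, 12 months and then annually post randomisation", with a tolerance of 28 days either side.

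**1.21.** A participant's trial ends at the "time of last follow-up visit (4 years post randomisation), participant withdrawal, or mortality, whichever occurs sooner".

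**1.27 and 1.27.5.** Revascularisation is to be done "no more than 18 weeks (+/- 28 days) from randomisation for elective cases", and within 6 weeks for urgent/ACS cases with the same tolerance.

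**1.26.1.** "Participants will be randomised on the day of consent in a 1:1 ratio", so consent and randomisation share a date.

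**1.43.** All randomised patients are analysed, "compared in the groups to which they were allocated regardless of treatment being received".

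**The concern.** The protocol gives sites two clocks for the same visits, and nothing in it says which prevails. A short gap between randomisation and procedure would be absorbed by the 28-day tolerance. The permitted gap for elective patients is too long for that.

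The data at stake are secondary and economic: EQ-5D-5L (and so QALYs), resource use and, through the shared visits, KCCQ and SAQ-7. If sites follow Table 1, a nominal 3-month score is taken at 3 months plus the patient's wait. Time since randomisation then varies between patients. If waits for CABG and PCI differ, it also differs between the randomised groups being compared. Table 1 taken alone gives no dates to a randomised patient who never has a procedure, and it places late-treated patients' 4-year visits after 1.21 has ended their participation.

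**Working it through.** **Inputs**
- Visit tolerance: 28 days either side (Table 1 and 1.20).
- Longest permitted wait (1.27, 1.27.5): elective 18 x 7 = 126 days, 126 + 28 = 154 with tolerance; ACS 6 x 7 = 42 days, 42 + 28 = 70 with tolerance.
- Conventions assumed here: 3 months = 91 days, 6 months = 183 days, 4 years = 1461 days. The 56-day threshold does not depend on them.

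**Overlap of the two windows.** Let a visit be due at T and let the procedure take place g days after randomisation. In days from randomisation:
- 1.20 allows T - 28 to T + 28.
- Table 1 allows T + g - 28 to T + g + 28.

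They share a day only if T + g - 28 <= T + 28, that is, g <= 56. This holds for every visit. Up to that point the number of common days is 57 - g. Beyond it, the Table 1 window opens g - 56 days after the 1.20 window closes.

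| Wait g (days) | Permitted as | Common days | 1.20 window closes to Table 1 window opens (days) |
|---|---|---|---|
| 42 | ACS limit | 15 | - |
| 56 | threshold | 1 | - |
| 57 | | 0 | 1 |
| 70 | ACS limit with tolerance | 0 | 14 |
| 126 | elective limit | 0 | 70 |
| 154 | elective limit with tolerance | 0 | 98 |

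The conflict therefore covers elective waits of 57-154 days (57-126 without using the tolerance) and ACS waits of 57-70 days, the latter only inside the tolerance.

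**3-month visit.** The 1.20 window is days 63-119.
- Procedure on day 126: Table 1 gives 126 + 63 = 189 to 126 + 119 = 245. The 1.20 window is wholly before the procedure. The first EQ-5D-5L after baseline is due on day 91 under 1.20 and on day 91 + 126 = 217 under Table 1.
- Procedure on day 92: Table 1 gives days 155-211, which is exactly the 6-month window of 1.20 (183 - 28 to 183 + 28). The same date could be labelled 3 months or 6 months.

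**4-year visit.** The 1.20 window is days 1433-1489. With a procedure on day 126, Table 1 gives days 1559-1615, opening 70 days after that window has closed.

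**Can the -30 to 0 column reconcile them?** If it were binding, g could not exceed 30 and the windows would share at least 57 - 30 = 27 days. But it would then forbid waits that 1.27 and 1.27.5 allow: even the basic ACS limit puts randomisation at Day -42, and the elective limit puts it at Day -126. Because consent is on the same day, Day -126 also falls outside the -90 to 0 column in which Table 1 places consent. The column cannot hold for the permitted waits and does not rescue the schedule.

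**Which clock does the rest of the text use?** Sections 1.20 and 1.21 use randomisation. The timetable in 1.23 agrees: recruitment ends at month 45 and the last visit is at 45 + 48 = 93, which leaves no allowance for a wait.

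**The case against.** The best case against is that this is one table label at odds with text that otherwise runs on randomisation. A statistician can use actual visit dates in the QALY area under the curve, and the economic time axis is then right. That stands for QALYs. It does not align the time points at which KCCQ and SAQ-7 are compared, and an analysis plan cannot supply visits that a site did not schedule.

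A second objection is that the protocol partly intends a procedure clock. Sections 1.17.2 and 1.31 list KCCQ and SAQ-7 at discharge and then at 3 months, and 1.37 sets survey reminders and interviews by weeks after the operation. This also stands: moving Table 1 to randomisation means that, in a late-treated patient, the 3-month questionnaire can come before the procedure and the discharge assessment. The fix has to say so.

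A reader might infer more than the documents support:
- *That never-treated patients have no follow-up dates at all.* Only Table 1 leaves them without dates. Section 1.20 gives them EQ-5D-5L and resource-use dates from randomisation, so the gap arises only if Table 1 is taken to override the text.
- *That any wait beyond 28 days puts the 4-year visit out of reach, or that visits run to about month 98, past data lock.* The first compares Table 1 with a bare day 1461 and ignores the tolerance in 1.20; with it, the threshold is 56 days, as for every other visit. The second combines the last day of recruitment, the full elective limit and the full tolerance, and assumes a visit that 1.21 would already have ruled out.
- *That KCCQ and SAQ-7 are contradicted as directly as EQ-5D-5L.* The text states no anchor specific to them. They are drawn in through the shared visits in footnote 1.
- *That the arms will be assessed at different times.* This follows only if waits differ by arm, and the protocol gives no waits by arm.

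**Conclusion.** The contradiction is real and nothing in the protocol resolves it. For elective patients it arises within the basic 18-week limit, from day 57 on; for ACS patients it arises only on days 57-70, inside the tolerance. At the elective limit of 126 days the two windows are 70 days apart, and with the full tolerance 98 days apart.

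The conflict is direct for EQ-5D-5L and resource use, and indirect for KCCQ and SAQ-7. The primary outcome is dated from randomisation in 1.17.1 and taken from routine records rather than visits, so this conflict does not touch it. The conclusion rests on reading Day 0 in Table 1 as the day of the procedure, which its column and the column after it both indicate. How many patients would be affected cannot be said, because the protocol gives no distribution of waits. The point should be corrected, since it concerns how data are collected and is cheap to put right, but it does not threaten the main result.

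**What to change.** Amend Table 1 so that all post-discharge follow-up columns are counted from randomisation, matching 1.20 and 1.21, and state that these dates apply to every randomised patient, treated or not. Show the index procedure as a floating visit within the limits of 1.27, and replace the -30 to 0 window for randomisation. Keep the procedure-to-discharge assessments and the 30-day events on the procedure date.

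Bring two other places into line. Reconcile the post-operation survey reminders and interviews in 1.37 with the chosen clock. In the KCCQ/SAQ-7 text of 1.17.2 and 1.31, note that in late-treated patients the 3-month questionnaire may precede the procedure and the discharge assessment.

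The cost is a wording amendment, plus resetting reminder dates in the data-capture app if they are built on the procedure date. No new data or procedures are needed. The small downside is that some early questionnaires will be completed before treatment, which is consistent with comparing patients as randomised.
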